### 2.3.1. Risk Assessment

Potential Risk of Clinical Significance	Summary of Data/Rationale for Risk	Mitigation Strategy
Study Intervention PF-07081532		
Gastrointestinal adverse reactions	
The potential risks are based on product labeling for injectable GLP-1R agonists (ie, liraglutide, exenatide, semaglutide and dulaglutide).
 
In addition, gastrointestinal adverse events, the majority of which were mild in severity, have been observed in the clinical program with PF-07081532.
	
The single dose and dose level administered in this study minimize any potential risk.
 
Participants are monitored during the clinical studies to prevent potential sequelae of any severe gastrointestinal reactions, eg, dehydration.

Hypoglycemia	
Clinical trials with injectable GLP-1R agonists have not demonstrated an increased risk for hypoglycemia. However, when administered in combination with anti-diabetic agents that are known to have an increased risk of hypoglycemia (such as insulin or sulfonylureas), an increased risk for hypoglycemia was observed.
	
The single dose and dose level administered in this study minimize any potential risk.
 
Study includes inpatient monitoring of the participants following administration of a single dose of the investigational product.

Increased heart rate	
Based on the product labeling for the injectable GLP-1R agonist liraglutide for obesity, mean increases in resting heart rate ranged 2 to 3 bpm in clinical trials, with some participants experiencing greater increases in resting heart rate, up to 10-20 bpm.
 
Following single dose administration of PF-07081532 in the completed FIH study, variable increases in heart rate were observed; the majority of individual values remained within normal ranges, and, throughout the study, no AEs or clinical symptoms related to vital sign parameters were reported.
	
The single dose and dose level administered in this study minimize any potential risk.
 
Study includes inpatient monitoring of the participants following administration of a single dose of the investigational product.

PFIZER CONFIDENTIAL

Potential Risk of Clinical Significance	Summary of Data/Rationale for Risk	Mitigation Strategy
Potential risks associated with long-term dosing of marketed GLP-1R agonists include thyroid C-cell tumors, pancreatitis, impairment in renal function, diabetic retinopathy complications, acute gallbladder disease,	The potential risks are based on product labeling for injectable GLP-1R agonists (ie, liraglutide, dulaglutide, exenatide and semaglutide); additional information is provided in the IB.	The single dose and dose level administered in this study minimize any potential risk.  Study includes inpatient monitoring of the participants following administration of a single dose of the investigational product.  Participants with a personal or family history of medullary thyroid carcinoma or MEN2; with acute pancreatitis or a history of chronic pancreatitis are not eligible for study entry.
Other		
Risk of COVID-19 exposure during study.	During the pandemic, study participants could be exposed to the SARS-CoV-2 virus during study participation. This could lead to increased health risk for this participant and others in the study.	Assessment of risk for, symptoms of or testing for COVID-19 may be performed at screening, admission to the CRU and/or at other times during the study at investigator discretion and according to local site policies.

PFIZER CONFIDENTIAL

### 2.3.2. Benefit Assessment

A single dose of PF-07081532 is not expected to provide any clinical benefit to study participants. This study is designed primarily to characterize the effect of varying degrees of hepatic impairment on the PK of PF-07081532 to support further clinical development of PF-07081532 as a potential treatment of T2DM. Results from this study will be used in conjunction with collective safety, tolerability, efficacy, and PK/PD data from other PF-07081532 studies to develop dosing recommendations for the target patient population with varying degrees of hepatic function.

### 2.3.3. Overall Benefit/Risk Conclusion

In line with the clinical profile of marketed GLP-1R agonists, the most frequently reported AEs in the 2 completed clinical studies with PF-07081532 administration have been in the Gastrointestinal Disorders SOC (Section 2.2.4). In addition, as has been reported for marketed GLP-1R agonists, modest increases in heart rate have been observed with PF-07081532 administration, with most heart rate values within the normal range. Based on available clinical data (Section 2.2.4 and current IB), a single 20 mg PF-07081532 dose is anticipated to be safe and well tolerated, including in participants with varying degrees of hepatic impairment, even if increased plasma concentrations were to be observed (Section 4.3).

Based on the profile of PF-07081532 observed in nonclinical and clinical studies to date, and taking into account the measures to minimize risk to study participants, the potential risk to the participants in this study is deemed to be minimal and is justified by the anticipated benefits that may be afforded to patients with varying degrees of hepatic impairment receiving PF-07081532 in the future.

## 3. OBJECTIVES AND ENDPOINTS

Objectives	Endpoints
Primary:	Primary:

To compare the PK of PF-07081532 following administration of a single oral dose in adult participants with varying degrees of hepatic impairment relative to age- and body weight-matched participants without hepatic impairment.

	

Plasma: <math>C_{max}</math>, <math>AUC_{inf}</math>, <math>AUC_{last}^*</math>, <math>fu</math>, <math>C_{max,u}</math>, <math>AUC_{inf,u}</math> and <math>AUC_{last,u}^*</math>, as data permit.

Secondary:	Secondary:

To evaluate the safety and tolerability of a single oral dose of PF-07081532 when administered to adult participants with varying degrees of hepatic impairment and in age- and body weight-matched participants without hepatic impairment.

	

Assessment of treatment emergent AEs, clinical laboratory abnormalities, vital signs, ECG parameters.

CCI	

Objectives	Endpoints
• CCI	[REDACTED]

\* AUClast and AUClast,u will be treated as primary endpoints if data do not permit robust estimation of AUCinf and AUCinf,u, otherwise they will be treated as tertiary endpoints.

## 4. STUDY DESIGN

### 4.1. Overall Design

This is an open-label, single-dose, parallel-group, multicenter study to investigate the effect of varying degrees of hepatic function on the plasma PK of PF-07081532 after a single, oral 20 mg dose administered in the fed state (standard breakfast). Safety and tolerability will be evaluated throughout the study. A total of approximately 24 participants with varying degrees of hepatic function will be dosed in the study as shown in Table 2. If recruitment of participants with severe hepatic impairment proves prohibitive, the number of participants to be enrolled in this group may be flexible (4-6 participants).

**Table 2. Hepatic Function Categories Based on Child-Pugh Score**

Group	Description	Child-Pugh Score	Number of Participants
1	Without hepatic impairment	Not Applicable	6 a
2	Mild hepatic impairment	Class A (5 to 6 points)	6
3	Moderate hepatic impairment	Class B (7 to 9 points)	6
4	Severe hepatic impairment	Class C (10 to 15 points)	6 b

- Additional participants may be dosed to a maximum of 8 participants to ensure mean age  $\pm 5$  years and mean body weight  $\pm 10$  kg of this group is aligned with the pooled average assessed when approximately  $\geq 75\%$  of participants are dosed across the other 3 groups.
- If recruitment proves to be prohibitive, study may dose 4-6 participants in this group.

Categorization of participants into Groups 2-4 will be done based on Child-Pugh scores determined, as described in [Appendix 11](#) at the screening visit.

### Staged Enrollment of Study Groups

Participants will be dosed in a staged manner as follows:

- Participants with moderate and severe hepatic impairment (Groups 3 and 4) will be enrolled first.
- Recruitment of participants with mild hepatic impairment (Group 2) will initiate when approximately 50% of the participants across Groups 3 and 4 have been dosed.

*Sponsor approval is required before proceeding with recruitment of Group 2.*

- An average value for age and weight for the 3 hepatic impairment groups (Groups 2-4) will be determined, and participants without hepatic impairment (Group 1) will be recruited to match the average demographics (at a minimum, age and weight, and as much as practically possible gender) across the pooled Groups 2-4.
- Recruitment for healthy participants in Group 1 (without hepatic impairment) may start when approximately 75% of total participants across Groups 2-4 (ie, approximately 12-13 participants) have been dosed.

***Sponsor approval is required before proceeding with recruitment of Group 1.***

Participants who prematurely discontinue before completing all assessments may be replaced, at the discretion of the investigator and sponsor study team.

The overall study design is presented as a schematic in [Section 1.2](#). For individual participants, the total duration of participation from the screening visit to the follow-up visit will range from approximately 5 weeks (minimum) to approximately 9 weeks (maximum). The study consists of an initial screening period of up to 28 days, a 7-day inpatient stay at the CRU which includes administration of a single oral dose of PF-07081532, and a follow up contact that will occur 28-35 days after PF-07081532 administration.

## 4.2. Scientific Rationale for Study Design

The purpose of this study is to characterize the effect of varying degrees of hepatic impairment on the PK, safety and tolerability of PF-07081532. PF-07081532 is an oral GLP-1R agonist that is currently being investigated as a chronic therapy to improve glycemic control in adult participants with T2DM. Based on review of the effect of hepatic impairment on human PK [CC1]

impaired hepatic function is generally associated with increased drug exposures in plasma CCI

[figure not shown]
As such, this study will enroll participants with varying degrees of hepatic impairment, and participants without hepatic impairment (matched for age as well as body weight and gender as much as practically possible) in order to allow a robust assessment of PK across the entire spectrum of hepatic function. A single dose of PF-07081532 is proposed, as single dose plasma PK of PF-07081532 is generally predictive of exposure upon repeated dosing.

Following administration of single oral doses of PF-07081532 under either fasted or fed conditions in Study C3991001 (non-Japanese cohorts), the arithmetic mean terminal  $t_{1/2}$  of PF-07081532 ranged approximately from 17 to 21 hours. Therefore, in this study, serial PK samples will be collected up to 144 hours post-dose in order to allow adequate characterization of the elimination phase of the plasma concentration-time profile should any increased half-life (up to 2-fold) in participants with varying degrees of hepatic impairment be observed.

Available PK data with PF-07081532 administered under fasted or fed conditions indicate that PF-07081532 may be administered without regard to food. In this study, a single dose of PF-07081532 will be administered with a standard breakfast to reflect the conditions for anticipated use of PF-07081532 in future trials and the target patient population.

[figure not shown]
PF-07081532 is extensively bound to plasma proteins with a fu of 0.000376 in humans and, as such, plasma protein binding may be affected in patients with chronic liver disease. To assess the in vivo protein binding of PF-07081532 with varying degrees of hepatic impairment, the fu of PF-07081532 will be determined in all participants at approximately the expected  $T_{max}$ .

CCI

In general, participants with normal hepatic function (Group 1) will abstain from concomitant treatments, except for the treatment of adverse events. Use of selected limited prescription and non-prescription medications may be permitted (refer to [Section 6.9](#) for details). Participants with impaired hepatic function (Groups 2, 3 and 4) are permitted to be on stable doses of background medications for the management of their concomitant medical condition(s) with some exclusions (see [Appendix 9](#) and [Appendix 10](#)).

CCI

To minimize the risks of COVID 19 related complications to participants and the study site personnel, assessment of risk for, symptoms of or testing for COVID-19 may be performed at screening, admission to the CRU and/or at other times during the study at investigator discretion and according to local site policies.

The Child-Pugh Classification (CPC; refer to [Appendix 11](#)) will be used to define the 3 groups of participants with varying degrees of hepatic impairment. This study will include participants with mild (Child-Pugh Class A, Group 2), moderate (Child-Pugh Class B, Group 3), and severe (Child-Pugh Class C, Group 4) hepatic impairment as well as demographically matched control participants without hepatic impairment (Group 1). All participants will be required to provide their own consent to participate in this study, hence participants with clinically active Grade 3 or Grade 4 encephalopathy will be excluded. However, participants who have a previous history of Grade 3 or 4 encephalopathy but are currently receiving an intervention (eg, lactulose or lactitol, alone or in combination with rifaximin, and/or neomycin) to manage their encephalopathy-related signs and symptoms are eligible provided the on-treatment encephalopathy grading at the screening visit is Grade 2 or lower, thereby permitting them to provide their own informed consent. Acknowledging the medical state of the population enrolled, certain eligibility criteria for participants with hepatic impairment are distinctly different, with no specific exclusion of participants with Hepatitis B and Hepatitis C in Groups 2, 3, or 4.

Although urinary recovery of PF-07081532 is low, with less than 0.2% of the dose recovered in the 24-hour dosing interval ([Section 2.2.4.2](#)), [CCI](#)

[\[REDACTED\]](#)  Therefore, in order to enable a robust assessment of the effect of hepatic impairment on PF-07081532 PK, participants will be excluded if there is concomitant clinical evidence of renal impairment, defined as eGFR <60 mL/min/1.73m^2.

#### **4.2.1. Choice of Contraception/Barrier Requirements**

Both women of childbearing potential, as well as those who are of non-childbearing potential, may be enrolled given the availability of EFD toxicity studies with PF-07081532. However, as marketed GLP-1R agonists are listed as contraindicated in pregnancy, measures will be taken to limit the risk of pregnancy in the female population enrolled (see [SoA](#) and [Section 10.4](#)).

The potential risk of exposure to PF-07081532 in a sexual partner of a male participant in this study via ejaculate is low, and therefore no contraception (condom) use in male participants is warranted. The calculated safety margin is  $\geq$ 100 fold between the estimated partner exposure due to seminal transfer and the NOAEL for serious manifestations of developmental toxicity in nonclinical studies. The safety margin of 100 fold is based on applying a 10 fold safety factor for interspecies extrapolation and a 10 fold safety factor for susceptible populations.

#### **4.2.2. Collection of Retained Research Samples**

Retained Research Samples will be collected and stored for further analyses which may, for example, provide greater understanding of the study intervention.

#### **4.3. Justification for Dose**

A single oral dose of 20 mg will be used in this study. This dose has been selected based on prior experience in clinical studies with PF-07081532 (Section 2.2.4) and also taking into account safety considerations for the participants with varying degrees of hepatic impairment in whom an increase in plasma PF-07081532 exposure may be observed.

In Study C3991001, a single dose of 30 mg was very well tolerated with an AE profile that did not differ from placebo. In the same study, single ascending doses up to 200 mg were tested and were considered safe and had a tolerability profile in line with expectations for the mechanism of action, with the majority of AEs being mild in severity and in the Gastrointestinal Disorders SOC (with nausea and vomiting the most frequently observed). For participants that experienced vomiting (observed at the 100 and 200 mg dose levels, with increased incidence at 200 mg), this generally occurred after the attainment of  $C_{max}$  and with no apparent impact on PF-07081532 exposure. In addition, the dose proposed in the current study (20 mg) reflects adequate safety margins compared to nonclinical toxicity studies. After accounting for species differences in plasma protein binding, this dose represents an exposure in participants with healthy hepatic function that is approximately [REDACTED] for  $C_{max}$  and AUC respectively, lower than the exposure observed at the NOAEL in the pivotal 9-month toxicology study in monkeys (Section 2.2.3). Given the above, it is anticipated that potential increases in plasma exposure in participants with varying degrees of hepatic impairment in the current study, if encountered, are not anticipated to pose an undue safety risk.

Although doses up to 260 mg QD may be evaluated in future clinical studies with PF-07081532, the proposed dose of 20 mg is viewed as appropriate for this study, given the potential of increased exposures in participants with hepatic impairment. Since no greater than dose-proportional increases in exposure of PF-07081532 have been observed over the range of clinical doses tested so far (up to single dose of 200 mg and up to 180 mg QD), the results from this study may be used to extrapolate and inform the effect of hepatic impairment on PK for doses exceeding 20 mg.

#### **4.4. End of Study Definition**

The end of the study is defined as the date of the follow up visit as shown in the SoA for the last participant in the trial globally.

A participant is considered to have completed the study if they have completed all phases of the study, including the follow up visit (telephone contact or onsite visit per Investigator discretion) as shown in the SoA.

### **5. STUDY POPULATION**

This study can fulfill its objectives only if appropriate participants are enrolled, including participants across diverse and representative racial and ethnic backgrounds. Use of a prescreening tool is utilized for study recruitment purposes, it will include collection of information that reflects the enrollment of a diverse participant population including, where

permitted under local regulations, age, sex, and race, and ethnicity. The following eligibility criteria are designed to select participants for whom participation in the study is considered appropriate. All relevant medical and nonmedical conditions should be taken into consideration when deciding whether a particular participant is suitable for this protocol.

Prospective approval of protocol deviations to recruitment and enrollment criteria, also known as protocol waivers or exemptions, is not permitted.

### **5.1. Inclusion Criteria**

Participants are eligible to be included in the study only if all of the following criteria apply:

#### **5.1.1. Participants in All Groups**

##### **Age and Sex:**

1. Male or female between the ages of 18 (or the minimum country-specific age of consent if >18) and 70 years, inclusive, at the screening visit.

Women may be of child-bearing potential, however, cannot be pregnant, breastfeeding, or planning to become pregnant while participating in the study. Refer to [Appendix 4](#) for reproductive criteria for male ([Section 10.4.1](#)) and female ([Section 10.4.2](#)) participants.

##### **Other Inclusion Criteria:**

2. Willing and able to comply with all scheduled visits, treatment plan, laboratory tests, lifestyle considerations (as described in [Section 5.3](#)), and other study procedures.
3. BMI of 17.5 to 38.0 kg/m^2, inclusive; and a total body weight >50 kg (110 lb), at the screening visit; with a single repeat assessment of total body weight (and hence BMI), *on a separate day* before Day -1 permitted to assess eligibility, if needed.
4. Capable of giving signed informed consent as described in [Appendix 1](#), which includes compliance with the requirements and restrictions listed in the ICD and in this protocol.

#### **5.1.2. Additional Inclusion Criteria for Group 1 *Only* (without Hepatic Impairment)**

1. At screening, no clinically relevant abnormalities identified by a detailed medical history, complete PE, including BP and pulse rate measurement, 12-lead ECG and clinical laboratory tests, as assessed by the sponsor approved laboratory.
2. At screening, participants must meet the demographic-matching criteria, including:
  - A body weight that is within  $\pm 10$  kg of the average of the pooled hepatic impairment groups (Groups 2, 3, and 4), as provided by the sponsor;

- An age that is within  $\pm 5$  years of the average of the pooled hepatic impairment groups (Groups 2, 3, and 4), as provided by the sponsor;
- *Attempts will be made* to ensure that the male-to-female distribution in Group 1 is comparable to that in the pooled hepatic impairment groups (Groups 2, 3, and 4).

3. No known or suspected hepatic impairment, and meet **all** the following criteria at screening, as assessed by the sponsor approved laboratory, with a single repeat permitted to assess eligibility, if needed:

- ALT  $\leq$  ULN;
- AST  $\leq$  ULN;
- T bili  $\leq$  ULN;

**NOTE:** Participants with a history of Gilbert syndrome (and hence elevated T bili) are eligible provided direct bilirubin level is  $\leq$  ULN **plus** ALT and AST are  $\leq$  ULN **plus** alkaline phosphatase, hemoglobin, and reticulocyte count are all  $\leq$  ULN.

- Albumin  $\leq$  ULN;
- PT  $\leq$  ULN.

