#### Additional for Group 1 Only (without Hepatic Impairment)

- At screening, no clinically relevant abnormalities identified by a detailed medical history, complete PE, including BP and pulse rate measurement, 12-lead ECG and clinical laboratory tests.

- At screening, meet the demographic-matching criteria, including body weight within  $\pm 10$  kg and age within  $\pm 5$  years, of the average of the pooled hepatic impairment groups, as provided by the sponsor.
- No known or suspected hepatic impairment and meet all the following criteria based on screening laboratory tests: ALT  $\leq$  ULN, AST  $\leq$  ULN, T bili  $\leq$  ULN, Albumin  $\leq$  ULN, PT  $\leq$  ULN.

*Additional for Groups 2, 3 & 4 Only (Hepatic Impairment)*

- Stable hepatic impairment that meets criteria for Class A, B, or C of the Child-Pugh classification with no clinically significant change in disease status within 28 days before screening.
- Stable concomitant medications for the management of individual participant's medical history.

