### **9.3.2.3. Supplementary Analyses**

Additional analysis using linear regression may be used to analyze the potential relationship between appropriate PK parameters (eg,  $AUC_{inf}$ ,  $AUC_{last}$ ,  $C_{max}$ ,  $f_u$ ,  $AUC_{inf,u}$ ,  $AUC_{last,u}$ ,  $C_{max,u}$ ) and hepatic function (eg, serum albumin concentration, PT or T bili). Plots of PK parameters (eg,  $AUC_{inf}$ ,  $AUC_{last}$ ,  $C_{max}$ ,  $f_u$ ,  $AUC_{inf,u}$ ,  $AUC_{last,u}$ ,  $C_{max,u}$ ) versus hepatic function will be constructed, with a regression line and 90% confidence region included. Estimates of the slope and intercept, together with a 90% CI, and the coefficient of determination (ie, R-squared and adj-R-squared) may be obtained from the model.

Additionally, as an exploratory analysis, age and body weight may be explored as additional covariates/factors in the models, as appropriate.

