**Table 7. Derivation of Child-Pugh Classification Score**

Assessment Parameters	Assigned score for observed findings		
	1 point	2 points	3 points
Encephalopathy grade a (refer to Table 8 below)	0	1 or 2	3 or 4 a
Ascites	Absent	Asymptomatic	Requiring intervention
Serum T bili, mg/dL	<2	2 to 3	>3
Serum albumin, g/dL	>3.5	2.8 to 3.5	<2.8
PT, sec prolonged	<4	4 to 6	>6

a. Participants with a prior history of Grade 3 or 4 encephalopathy who are *currently* receiving an intervention [eg, lactulose or lactitol, alone or in combination with rifaximin, and/or neomycin] to manage encephalopathy related signs and symptoms should be scored for encephalopathy grading *based on their presentation while on intervention at the screening visit* and can be included in Study C3991009 as long as they do *not* have clinically active Grade 3 or 4 encephalopathy.

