5.2.4. Linear Regression PK Parameters versus Hepatic Function

Linear regression will be used to analyze the potential relationship between appropriate PK parameters (eg, AUC_{inf} , AUC_{last} , C_{max} , f_u , $AUC_{inf,u}$, $AUC_{last,u}$, $C_{max,u}$) and hepatic function as a continuous explanatory variable (using either continuous serum albumin, prothrombin time or total bilirubin, each modelled separately). Estimates of the slope and intercept, together

[figure not shown]
Pfizer Confidential

with a 90% CI, and the coefficient of determination (i.e. R-squared and adj-R-squared) may be obtained from the model. Example SAS code is given in Appendix 1.

Residuals from the models will be examined for normality and the presence of outliers via visual inspection of plots of residuals vs predicted values and normal probability plots of residuals but these will not be included in the clinical study report. If there are major deviations from normality or outliers (where studentized residuals are greater than 3 or less than - 3) then the effect of these on the conclusions may be investigated through alternative transformations and/or analyses excluding outliers. Alternative model structure may also be considered. Justification for any alternative to the planned analysis will be given in the report of the study if applicable.

CCI

CCI

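### Group 1 eligibility caps albumin from above and sets no lower limit, so a low-albumin control is kept out only by judgement

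*Protocol*

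**What the plan says.** Protocol 5.1 makes the inclusion criteria cumulative: "Participants are eligible to be included in the study only if all of the following criteria apply". For Group 1, two criteria in 5.1.2 bear on liver function.

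- Criterion 1 asks for "no clinically relevant abnormalities identified by a detailed medical history", physical examination, ECG and laboratory tests. It gives no numeric limits.
- Criterion 3 begins "No known or suspected hepatic impairment, and meet" and lists ALT, AST, total bilirubin, albumin and PT, each at or below ULN, with one repeat allowed.

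The Synopsis has the same five limits, introduced by "No known or suspected hepatic impairment and meet all the following criteria based on screening laboratory tests". Neither place gives albumin a lower bound.

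Elsewhere the documents treat low albumin as the abnormal direction. In Appendix 11, Table 7, the row "Serum albumin, g/dL" gives 1 point above 3.5, 2 points for 2.8 to 3.5 and 3 points below 2.8. Protocol 9.3.2.3 names measures of "hepatic function (eg, serum albumin concentration, PT or T bili") for the supplementary regression. SAP 5.2.4 does the same, "using either continuous serum albumin, prothrombin time or total bilirubin, each modelled separately".

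**The concern.** The numeric list is there to put objective limits behind the statement that a control has no hepatic impairment. For albumin it does not do so: it turns away only people with high albumin and passes any low value. A site could also reasonably read a low result as satisfying the stated limit.

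Binding matters in this study. Protocol 4.2 gives a human fu of 0.000376 and says that chronic liver disease may affect binding. fu is a listed primary endpoint, and the unbound exposure parameters are fu times the total parameters (Protocol Table 3). Each of the three impairment groups is compared with Group 1 alone, which has 6 participants and at most 8. A low-albumin control would tend to raise the Reference fu and pull the Test/Reference fu ratio toward 1.

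**Working it through.** **Direction of the limits.** ALT, AST, bilirubin and PT rise with impairment, so an upper bound screens for it. Albumin falls, so an upper bound does not. As an illustration, take albumin below 2.8 g/dL with the other four Child-Pugh items at 1 point each: 3 + 1 + 1 + 1 + 1 = 7, which is in the Class B range. If ALT, AST, bilirubin and PT are within ULN, that person meets every numeric limit in criterion 3. Child-Pugh class does not apply to Group 1, so this shows only which way the error runs.

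**Is there a numeric limit elsewhere?** The other relevant provisions are criterion 1, the opening condition of criterion 3, the all-groups exclusion for other medical conditions or laboratory abnormalities (Protocol 5.2.1, item 5) and the Group 1 chronic liver disease exclusion (5.2.2, item 1). None contains an albumin value.

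**Plan's own figure.** There is none to reproduce. The entries of Protocol Table 4 and its SD are blacked out.

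**Size of the shift in Reference fu**

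- From the documents: n = 6, maximum 8; analysis on the natural-log scale with Group 1 as Reference (Protocol 9.3.2.2).
- Assumed: albumin is the main binding protein; fu is proportional to 1/albumin; typical control albumin is 4.0 to 4.5 g/dL.
- Formula, for one low-albumin control among n: shift in geometric mean fu = (typical albumin / low albumin)^(1/n).
- Example: (4.0/3.4)^(1/6) = 1.027 and (4.5/3.4)^(1/6) = 1.048.

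| Albumin of the one control | n = 6 | n = 8 |
|---|---|---|
| 3.4 g/dL | +2.7 to +4.8% | +2.1 to +3.6% |
| 3.0 g/dL | +4.9 to +7.0% | +3.7 to +5.2% |
| 2.8 g/dL | +6.1 to +8.2% | +4.6 to +6.1% |

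With two such controls the exponent is 2/n. Over 2.8 to 3.4 g/dL this gives about +6 to +17% for n = 6 and +4 to +13% for n = 8.

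**Effect on the fu ratio.** Take an illustrative true ratio of 1.40 and one low control among six. At 3.4 g/dL the expected estimate is 1.40/1.027 = 1.36 to 1.40/1.048 = 1.34. At 3.0 g/dL it is 1.40/1.049 = 1.33 to 1.40/1.070 = 1.31.

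**Effect on exposure.** Assume AUC = Dose/(fu × CLint). Reference total AUC is then divided by the same factor, so the total AUC ratio rises by the percentages in the table. Unbound AUC, fu × AUC = Dose/CLint, does not change.

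**Comparison with precision.** For 6 versus 6 in the four-group ANOVA (20 df), the 90% CI half-width on the log scale is t(0.95, 20) × SD × √(1/6 + 1/6) = 1.725 × 0.577 × SD = 0.996 × SD. For assumed SDs of 0.2 to 0.6 the interval is the estimate ×/÷ 1.22 to ×/÷ 1.82. The largest one-control shift, ln 1.082 = 0.079, exceeds the half-width only if the SD is below about 0.08.

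**The case against.** The strongest reply is that such a control is unlikely to be enrolled. Albumin of 3.0 g/dL would have to be judged not clinically relevant under criterion 1 and not suspicious of hepatic impairment under criterion 3. It would also have to pass the two exclusions named above. All of these are mandatory, and Protocol 5 rules out waivers. This stands as far as it goes. The more plausible gap is a slightly low value, so the 3.4 g/dL row is the better guide than the lower two.

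The shift is also smaller than the sampling error over the assumed SDs, and the study is estimation only, with no hypothesis tests or decision rules. That stands too, with one caveat: the readable text gives no SD for fu. Sampling error is also not a reason to leave a known directional error in place.

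The pharmacokinetic consequence rests on assumptions. The protocol refers to plasma proteins and does not, in its readable text, name albumin as the main one. Unbound AUC would be largely unaffected under the clearance model used here. Both points limit the size of the concern, but the error in the criterion does not depend on them.

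The planned regression on albumin could reveal a low-albumin control. It would not correct the ANOVA ratio.

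**Conclusion.** The concern holds. A mandatory numeric criterion for the only Reference group is bounded on the wrong side, in both places where it appears. Exclusion of a low-albumin control therefore depends on judgement. Criterion 1 does not say who decides clinical relevance; item 5 of 5.2.1 refers to the investigator's judgement.

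The direction of the possible bias is Reference fu up, fu ratio toward 1 and, under the oral-clearance assumption, total AUC ratio up. With one such control the size is about 3 to 8% for n = 6 and 2 to 6% for n = 8, conditional on enrolment and on the stated binding assumptions. Confidence is high for the wording error and lower for the size of the bias. No sample size or precision statement is affected. It should be fixed because the error is clear and the correction is cheap.

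**What to change.** In Protocol 5.1.2, criterion 3, and in the Synopsis, replace the albumin limit with albumin ≥ LLN. The documents do not give the laboratory's LLN, so check it against the 3.5 g/dL cut in Table 7.

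As a secondary wording correction in the same criterion, the Gilbert syndrome note also caps hemoglobin at ULN, although hemolysis lowers it. Give hemoglobin a lower bound (≥ LLN) and leave the alkaline phosphatase and reticulocyte limits as they are. The reticulocyte and direct bilirubin limits already give some protection there.

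The cost is a protocol amendment to these two places and possibly a few more Group 1 screen failures. Albumin and hemoglobin are already in the laboratory panel (Protocol Table 5). Timing is favourable: "Recruitment for healthy participants in Group 1 (without hepatic impairment) may start when approximately 75% of total participants" in Groups 2-4 have been dosed, and sponsor approval is needed at that step, so the change can be in force before any control is recruited. The SAP does not repeat the criterion and needs no change.
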